6.2.6.2. ADA titer

For patients who are ADA ever positive, the maximum observed ADA titer for a patient will be summarized, overall and by ADA subcategories (baseline ADA positive, treatment-boosted ADA, treatment-induced ADA, transient ADA response, persistent ADA response) of patients having each discrete maximum titer value will be tabulated. The denominator to calculate the percentages will be the total number of patients in the associated ADA subcategory.

For patients with treatment-induced ADA, a cross tabulation of duration of ADA response and maximum ADA titer will be provided. The following categories for duration of ADA response will be used: ≤ 1 , >1 to ≤ 3 , >3 to ≤ 5 , >5 to ≤ 7 , >7 to ≤ 13 , >13 to ≤ 16 , >16 to ≤ 25 , >25 weeks. In this categorization, the censoring in duration of ADA response is ignored.

6.2.6.3. Analysis of PK and safety by immunogenicity status

The following ADA and nAb status will be used for the analyses described below.

ADA

- ADA ever-positive versus ADA never-positive
- ADA: treatment-induced ADA versus ADA never-positive or baseline ADA positive

nAb

- nAb ever-positive versus nAb never-positive
- nAb: treatment-induced nAb versus nAb never-positive or baseline nAb positive

Data listings will include immunogenicity data together with relevant PK, safety and efficacy data.

PK parameters and immunogenicity status

The following analyses will include patients in both the immunogenicity analysis set and in the PK parameter analysis set. The PK endpoints pertinent to the immunogenicity analyses are C_{trough} and C_{max} .

Blood samples for avelumab PK will be collected pre-dose and at the end of infusion (immediately before the end of avelumab infusion) on Day 1 and Day 15 of Cycles 1 – 3, and then pre-dose and at the end of avelumab infusion) on Day 1 of Cycle 5, 7, 9, 11 and 13.

C_{trough} and C_{max} will be summarized descriptively (n, mean, SD, CV, median, minimum, maximum, geometric mean, its associated CV, and 95% CI) by nominal time and ADA status. Linear-linear plots of mean and median for C_{trough} and C_{max} over nominal time and by ADA status will be presented.

Among patients with treatment-induced ADA, analyses will be conducted to assess whether C_{trough} and C_{max} have any changes before and after the first positive ADA assessment. To be included in this analysis, patients must have the same PK parameter available both before and after the first positive ADA assessment. Relative PK day will be calculated as:

$$(\text{PK assessment nominal day}) - (\text{first positive ADA assessment nominal day}).$$

Nominal day is the protocol scheduled timing for an assessment. For example, if C_{trough} is collected on Day 1 of Cycle 2 and the first positive ADA result is observed on Day 1 of Cycle 3, then the relative PK day for this C_{trough} is -28. Linear-linear plots of mean and median for C_{trough} and C_{max} over relative PK day will be presented.

As data permit, the analyses described above will be repeated for nAb.

Safety and immunogenicity status

The following analyses will include patients in the immunogenicity analysis set.

The frequency (number and percentage) of patients with each of the following will be presented by ADA status.

- TEAEs, by SOC and PT
- TEAEs leading to discontinuation of avelumab, by SOC and PT

- TEAEs leading to dose reduction of avelumab, by SOC and PT
- Grade ≥ 3 TEAEs, by SOC and PT
- SAEs, by SOC and PT
- IRRs, by PT

For patients who had at least one IRR and have treatment-induced ADA, time related to first onset of an IRR (infusion 1, infusion 2, infusion 3, infusion 4 or later) will be summarized taking into account whether the IRR occurred on or after the first ADA positive assessment or whether the IRR occurred before the first ADA positive assessment.

As data permit, the analyses described above will be repeated for nAb.

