| 
21. Anti-Avelumab Antibodies (Anti-Drug Antibodies, ADAs) and Neutralizing Antibodies (Nab): Arm A ONLY. One blood sample (3.5 mL) for anti-avelumab antibodies (and simultaneous pharmacokinetic draws for measurement of avelumab) will be collected at the End of Treatment and 30 day Follow-up visits. All the samples that are positive for ADA may also undergo characterization for Nab.
 |

PROTOCOL AMENDMENT 6: SCHEDULE OF ACTIVITIES FOR STUDY TREATMENT, END OF TREATMENT AND FOLLOW-UP PERIODS

| Visit Identifiers ¹ | Avelumab plus BSC (1 cycle = 4 weeks) | | End of Treatment/ Withdrawal (±3 days) ² | Short-Term Follow-Up ³ | | |
|---|---|---------------------|---|--|--|--|
| | Day 1 (±3 days) | Day 15 (±3 days) | | 30 days (±3 days) After Last Dose of Avelumab | 60 days (±3 days) After Last Dose of Avelumab | 90 days (±3 days) After Last Dose of Avelumab |
| Clinical Assessments | | | | | | |
| Physical Examination ⁴ | Assessment not required per protocol but may be performed as clinically necessary | | | | | |
| ECOG Performance Status ⁴ | Assessment not required per protocol but may be performed as clinically necessary | | | | | |
| Vital Signs ⁴ | Assessment not required per protocol but may be performed as clinically necessary | | | | | |
| Weight ⁵ | X | X | | | | |
| Contraception Check ^{4,6} | X | X | X | X | | |
| Laboratory Studies | | | | | | |
| Hematology ^{4,7} | X | X | X | X | X | X |
| Blood Chemistry ^{4,7} | X | X | X | X | X | X |
| Thyroid Function and ACTH Tests ^{4,8} | X (at odd number cycle only) | | X | X | X | X |
| Serum/Urine Pregnancy Test ^{4,9} | X | X | X | X | | |
| Urinalysis ⁴ | Assessment not required per protocol but may be performed as clinically necessary | | | | | |
| 12-Lead ECG ^{4,10} | Assessment not required per protocol but may be performed as clinically necessary | | | | | |
| Other Assessments | | | | | | |
| Tumor Assessments (including scans) ¹¹ | As per local standard of care and when progression is suspected | | | | | |
| Adverse Events ¹² | X | X | X | X | X | X |
| Concomitant Medications/Treatments ¹³ | Assessment not required per protocol but may be performed as clinically necessary | | | | | |
| Study Treatment | | | | | | |
| Avelumab ¹⁴ | X | X | | | | |

ACTH = adrenocorticotropic hormone; BSC = best supportive care; CR = crossover; ECG = electrocardiogram; ECOG = Eastern Cooperative Oncology Group

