4.3.4. Immunogenicity analysis set

The immunogenicity analysis set is a subset of the safety analysis set and will include patients who have at least one ADA/nAb sample collected for avelumab in Arm A.

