5.3.1.1. Pharmacokinetic concentrations

Concentrations Below the Limit of Quantification

For all calculations, figures and estimation of individual pharmacokinetic parameters, all concentrations assayed as below the level of quantification (BLQ) will be set to zero. The BLQ values will be excluded from calculations of geometric means and their confidence intervals (CIs). A statement similar to 'All values reported as BLQ have been replaced with zero' should be included as a footnote to the appropriate tables and figures.

Deviations, Missing Concentrations and Anomalous Values

In summary tables and plots of median profiles, concentrations will be set to missing if one of the following cases is true:

1. A concentration has been reported as ND (ie, not done) or NS (ie, no sample);
2. A deviation in sampling time is of sufficient concern or a concentration has been flagged as anomalous by the clinical pharmacologist.

Summary statistics will not be presented at a particular time point if more than 50% of the data are missing. For analysis of pharmacokinetic concentrations, no values will be imputed for missing data.

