6.2.6. Endpoints for Immunogenicity Data of Avelumab

All analyses described below are performed for Arm A.

Blood samples (3.5 mL SST tube per timepoint) for evaluation of avelumab immunogenicity will be collected from Arm A patients within 2 hours before the start of the avelumab infusion on Day 1 and Day 15 of Cycles 1 through 3 and then on Day 1 of Cycle 5, 7, 9, 11 and 13. Immunogenicity blood samples will be assayed for anti avelumab antibodies using a validated analytical method. All of the samples that are positive for ADA may also undergo characterization for nAb.

Patients will be characterized into different ADA categories based on the criteria defined in [Table 14](#).

Table 14. Patients Characterized Based on Anti-Drug Antibody Results (ADA Status)

Category	Definition	Patients at Risk (Denominator for Incidence)
ADA never-positive	No positive ADA results at any time point; ADA-negative patients (titer < cutpoint)	Number of patients with at least one valid ADA result at any time point
ADA ever-positive	At least one positive ADA result at any time point; ADA-positive patients (titer ≥ cutpoint)	Number of patients with at least one valid ADA result at any time point
Baseline ADA positive	A positive ADA result at baseline	Number of patients with valid baseline ADA result
Treatment-boosted ADA	A positive ADA result at baseline and the titer ≥ 8×baseline titer at least once after treatment with avelumab	Number of patients with valid baseline ADA results and at least one valid post-baseline ADA result
Treatment-induced ADA	Patient is ADA-negative at baseline and has at least one positive post-baseline ADA result; or if patient does not have a baseline sample, the patient has at least one positive past-baseline ADA result	Number of patients with at least one valid post-baseline ADA result and without positive baseline ADA result (including missing, NR)
Transient ADA response	If patients with treatment-induced ADA have (a single positive ADA result or duration between first and last positive result < 16 weeks) and ADA result at the last assessment is not positive.	Number of patients with at least one valid post-baseline ADA result and without positive baseline ADA result (including missing, NR)

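### AE tables by ADA status group patients on results acquired during treatment, so time on treatment can create differences that ADA did not cause

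*SAP*

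**What the plan says.** SAP 6.2.6.3 sets two ADA contrasts: "ADA ever-positive versus ADA never-positive" and "ADA: treatment-induced ADA versus ADA never-positive or baseline ADA positive". Table 14 in SAP 6.2.6 defines ever-positive as "At least one positive ADA result at any time point". The neutralizing antibody (nAb) groups are built the same way and are analysed as data permit.

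For safety, the section says: "The frequency (number and percentage) of patients with each of the following will be presented by ADA status". The list covers all TEAEs, TEAEs leading to discontinuation or dose reduction of avelumab, Grade ≥3 TEAEs, SAEs and infusion-related reactions (IRRs). The analysis set in SAP 4.3.4 is "patients who have at least one ADA/nAb sample collected for avelumab in Arm A", so a patient with a single early negative sample counts as never-positive.

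On-treatment samples are taken on "Day 1 and Day 15 of Cycles 1 through 3 and then on Day 1 of Cycle 5, 7, 9, 11 and 13" (SAP 6.2.6). The protocol's follow-up Schedule of Activities adds samples that "will be collected at the End of Treatment and 30 day Follow-up visits". The AE window (SAP 5.2.7) runs from first dose to 30 days after last dose, or to the day before new anti-cancer drug therapy if that is earlier.

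Two analyses in SAP 6.2.6.3 respect the order of events. C_trough and C_max are compared before and after the first positive result. First IRR onset is split in the same way, but only among treatment-induced ADA patients who had an IRR.

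**The concern.** ADA status is learned over time but applied from the first dose. Time on treatment drives both sides of the table: it gives more samples in which to turn positive, and a longer window in which to have an AE. An AE in Cycle 1 of a patient who first tests positive in Cycle 7 is counted as an ADA-positive AE. This is immortal-time bias. The summary is a raw percentage of patients, with no person-time, landmark or time-updated status to correct it.

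A second mechanism works the other way for one category. A patient who stops early because of an AE has less time to become positive, so such patients gather in the never-positive column.

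Immunogenicity is a secondary objective, and these are the SAP's only AE tables that set ADA-positive patients beside never-positive ones. Readers will compare the columns and may conclude that ADA affects tolerability.

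**Working it through.** **Documented figure.** The plan states no AE frequency by ADA status. The nearest figures are the IRR data in Protocol 1.2.2.1: onset at infusions 1 to 4 in 91, 35, 9 and 3 patients. 91 + 35 + 9 + 3 = 138, and 138/717 = 19.2%, as stated. Infusions 1 and 2 account for 126/138 = 91%.

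**Inputs from the documents.** ADA samples on days 1, 15, 29, 43, 57, 71, 113, 169, 225, 281 and 337, at End of Treatment and 30 days after last dose; dosing every 2 weeks; AE window to last dose + 30 days.

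**Assumptions, not in the documents.**
- Median treatment 3, 6 or 9 months (exponential).
- ADA incidence parameter 5% to 20%.
- ADA onset at a median of 4 weeks, a median of 12 weeks, or at constant hazard over treatment.
- AE hazard 0.03 or 0.10 per month.
- 10% of patients with an AE that stops treatment, either front-loaded (mean 42 days) or at constant hazard.
- Runs with and without a data cut-off. New anti-cancer therapy was not modelled.

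**Method.** 400,000 patients per scenario, with ADA having no effect on AEs, tabulated as the SAP plans.

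**Example.** Median treatment 6 months, AE hazard 0.10 per month, front-loaded stops, no data cut-off:

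| ADA onset | Median AE window, ever- vs never-positive (months) | With AE, ever- vs never-positive | Difference (points) | AE leading to discontinuation, ever- vs never-positive |
|---|---|---|---|---|
| Median 4 weeks | 6.5 vs 5.6 | 50.2% vs 46.6% | +3.6 | 6.8% vs 8.8% |
| Median 12 weeks | 8.8 vs 5.6 | 56.6% vs 46.4% | +10.2 | 4.3% vs 8.9% |
| Constant hazard | 13.4 vs 5.1 | 68.5% vs 44.7% | +23.9 (unrounded inputs) | 2.3% vs 9.4% |

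**Hand check.** For a window of T months, P(AE) = 1 − exp(−hT). In the 20% ADA, constant-hazard run the median windows are 12.9 and 5.6 months. With h = 0.10, 1 − exp(−1.29) = 72% and 1 − exp(−0.56) = 43%. The simulation, which uses the full spread of windows, gave 68.6% and 45.1%.

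**All scenarios, accumulating AEs.** Always higher in ever-positive patients: +1 to +4 points (4 weeks), +3 to +11 (12 weeks), +6 to +26 (constant hazard). A further no-effect simulation at 0.06 per month gave about 2–3, 7–8 and 13–24 points.

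**All scenarios, AEs leading to discontinuation.** If front-loaded, from −1.3 points (6.3% vs 7.6%; onset 4 weeks, median treatment 3 months) to −8.2 points (1.6% vs 9.8%; constant ADA hazard, median treatment 9 months). At constant hazard the gap is under 1 point throughout.

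**IRRs.** In the earlier data 17 of 717 patients stopped for an IRR. Suppose all 17 end up never-positive and 10% of patients (71.7) are positive. IRR share in positives = (138 − 17)/(717 − 17) = 121/700 = 17.3%. In never-positives = (138 − 0.173 × 71.7)/(717 − 71.7) = 125.6/645.3 = 19.5%. The gap is about −2 points.

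**Effect of the late samples.** Without the End of Treatment and 30-day samples, the +3.6 in the first row becomes +8.4.

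**Does updating status remove the bias?** Counting events and time before the first positive sample as negative gives no-effect rate ratios of 0.97 to 1.03 in every scenario above, where the AE hazard is constant. With a hazard five times higher in the first 28 days, crude rates per patient-month gave a no-effect ratio of 0.54 to 0.69, because positive time falls later. After day 28 the ratio was about 1.0. The comparison therefore has to be made at the same time since first dose.

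**The case against.** The tables carry no test, confidence interval or claim, and SAP 3.5.1 treats safety analyses as generally exploratory. Sampling is two-weekly through Cycle 3, and the End of Treatment and 30-day samples give early stoppers further chances to test positive. IRR onset is split by timing, time to ADA is summarized (SAP 6.2.6.1), and PK is compared before and after the first positive. Baseline-positive patients do have a status known at the start.

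All of this stands, and it limits both the size and the consequence. It does not remove the defect. The IRR split has no never-positive comparator, and the other AE categories have no timing safeguard. A descriptive table still invites comparison of its columns.

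Three stronger readings are tempting but not supported:
- *Longer treatment alone distorts in both directions.* It only raises cumulative AE percentages in ever-positive patients. The opposite sign needs early AEs that stop treatment, and it disappears when such stops occur at constant hazard.
- *The distortion must be large.* That depends on ADA timing and treatment duration, which the documents do not give. With onset within weeks it is a few points.
- *Excluding concentrations below quantification (BLQ) from geometric means hides a loss of exposure.* SAP 5.3.1.1 keeps them as zero in other calculations. SAP 6.2.6.3 also reports mean, median and minimum by ADA status, and plots means and medians before and after the first positive. If 10% to 20% of troughs were BLQ and the rest 20 µg/mL (assumed), the arithmetic mean would fall to 18 or 16 and the minimum to 0.

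**Conclusion.** The concern holds in limited form. The planned AE percentages by ADA or nAb status cannot be read as an effect of ADA, because status from any time point is applied from first dose and the AE window lengthens with treatment. With no true effect, accumulating AEs look more frequent in ever-positive patients by about 1–4, 3–11 or 6–26 points for ADA onset at 4 weeks, at 12 weeks or steadily. AEs leading to discontinuation look about 1–8 points less frequent if front-loaded, with essentially no gap at constant hazard. The direction of the first effect follows from the plan's definitions; every size rests on the assumptions listed. The issue is confined to descriptive secondary safety tables. It merits a correction to the SAP and does not affect the primary analysis.

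**What to change.** For the overall categories only (any TEAE, Grade ≥3 TEAE, SAE, TEAE leading to discontinuation), add an analysis in which ADA or nAb status changes at the first positive sample and never-positive patients contribute negative time throughout. Use a Cox model on time since first dose with status as a time-dependent covariate, or rates stratified by time since first dose. Do not use crude rates per patient-month, which are biased when AEs cluster early.

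Show treatment duration and number of ADA samples by group. Footnote the existing tables by system organ class and preferred term as not showing an effect of ADA. For PK by ADA status, print the number of BLQ values beside each geometric mean; no substitution rule is needed.

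The cost is SAP wording and modest programming, since the dates of first dose, AE onset and ADA samples are already collected. Limits to state: few events in ADA-positive time, and first-positive dates that lag true onset once sampling is 8-weekly (from Cycle 5).

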6.2.7. PRO endpoints

6.2.7.1. PRO Instruments

Patient-reported outcomes of HRQoL will be evaluated using NCCN-FACT Bladder Symptom Index (FBISI-18) and EQ-5D-5L. A 9-item subscale of the FBISI-18 known as the FBISI-Disease Related Symptoms-Physical subscale (FBISI-DRS-P) measuring advanced bladder cancer disease related symptoms will be used to define time to deterioration.

All PRO analyses will be based on FAS. Descriptive summaries will include all the assessments per schedule of assessment from baseline to the last PRO assessment. For time-to-event analysis and random coefficient models will include assessments from baseline up to EOT (not including EOT).

6.2.7.2. Scoring Procedure

The NCCN-FACT FBISI-18 and EQ-5D-5L will be scored according to their respective validation papers and user's guides. Missing values in the instruments will also be handled following the guidance from their respective User Manuals. The NCCN-FACT FBISI-18 questionnaire allows for the calculation of an overall score and scores for four subscales; Disease Related Symptoms – Physical (DRS-P), Disease Related Symptoms – Emotional (DRS-E), Treatment Side Effects (TSE), and Functional and Well-being (F/WB). For the NCCN-FACT FBISI-18 multi-item scales, the score may be imputed as the mean of the non-missing questions if at least half the questions in that scale are answered. For EQ-5D-5L, the entire score for that cycle is deemed missing if the answer to any one of the 5 dimensions is missing. In addition to items for the 5 dimensions, the EQ-5D-5L contains a single visual analog scale (EQ-VAS) item that is used to assess the respondent's self-reported health status.

6.2.7.3. Instrument Compliance Rates

For each treatment arm and at each time point, the number and percentage of patients who complete the NCCN-FACT FBISI-18, EQ-VAS and EQ-5D-5L will be summarized, as will the reasons for non-completion of these measures. An instrument is considered complete if at least one item was answered by the patient.

6.2.7.4. Descriptive Summary

Separate tables will be used to summarize, for each treatment arm, the mean (and SD), and median (and range) of absolute scores, and the mean (and 95% CI) of change from baseline of the NCCN-FACT FBISI-18, and all subscales (DRS-P, DRS-E, TSE, and F/WB) of the NCCN-FACT FBISI-18, the EQ-5D-5L, and EQ-VAS at each time point. A line chart depicting the means along with 95% CIs over time will be provided for each scale in each treatment arm.

For the EQ-5D-5L, EQ-VAS, NCCN-FACT FBISI-18, and subscales of the NCCN-FACT FBISI-18 (DRS-P, DRS-E, TSE, F/WB), for each post-baseline visit, a means score and mean change from baseline scores will be generated for each treatment arm, adjusting for baseline differences in the treatment arms. The adjusted means (ie LS-MEANS) will be obtained from ANCOVA model that included baseline score and treatment as independent variables. For each per-visit analysis, the n, LS-mean, standard error, and 95% CI will be reported.

A figure will be provided for the cumulative patient disposition by treatment arm per PRO assessment window (ie every 28-day cycle) for all scheduled assessments (Day 1 of each cycle) using the following categories:

- PRO assessment expected;
- PRO assessment not expected due to progression;
- PRO assessment not expected due to death;
- PRO assessment not expected due to other reasons.

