3.4.2. Baseline Characteristics

Randomization is stratified by the following, as recorded in the Interactive Response Technology (IRT) system:

- Best response to first-line chemotherapy (CR or PR vs. SD)
- Metastatic disease site (visceral vs. non-visceral) at the time of initiating first-line chemotherapy. The ‘non-visceral’ stratum includes patients with locally-advanced disease as well as patients with only non-visceral disease.

The primary analyses of OS will be stratified by these randomization stratification factors.

Other baseline characteristics (including demographics, physical measurements, disease history and prior anti-cancer therapies) are described in [Section 6.5.1](#). These baseline characteristics are not planned to be included as stratification variables or covariates in statistical models unless otherwise specified in [Section 6](#).

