6.2.7.5. Time-to-Deterioration Analysis

A 3-point change in FBISI-DRS-P has been established as clinically meaningful. Time to deterioration (TTD) is defined as the time from the date of randomization to the first time the patient's score shows a 3 point or greater decrease from baseline in FBISI-DRS-P for 2 consecutive assessments.

Patients will be censored at the last time when they completed the assessment if they have not deteriorated.

TTD will be analyzed by a log-rank test stratified by randomization stratification factors. The time to deterioration in each treatment arm will be summarized using the Kaplan-Meier method and displayed graphically where appropriate. Confidence intervals (CIs) for the 25th, 50th and 75th percentiles will be reported. The Cox proportional hazards model will be fitted to compute the treatment hazard ratios and the corresponding 95% CI.

Sensitivity analyses based on a 2- and 4-point decrease from baseline in FBISI-DRS-P will also be conducted to assess the robustness of the TTD analyses. Cumulative distribution plots of FBISI-DRS-P will also be presented on Day 1 of Cycles 2, 4 and 6.

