6.2.7.6. Random Coefficient Models

Random coefficient models will be carried out for the NCCN-FACT FBISI-18 and all subscales (DRS-P, DRS-E, TSE, and F/WB), EQ-5D-5L, and EQ-VAS using PROC MIXED. Outcomes are PRO post-baseline scores and the predictors are the corresponding baseline PRO score, treatment, time (treated as a continuous variable), and treatment-by-time interaction. Intercept and time are considered as random effects particular to each patient. All available data for each patient should be used in the analyses. All parameter estimates should be obtained using restricted maximum likelihood. The unstructured covariance structure should be used to define covariance between random effects (using option “Type=UN” as a part of the RANDOM statement in PROC MIXED). For the degrees-of-freedom calculations the Kenward and Roger algorithm should be used (using option “ddfm = kr” as a part of the MODEL statement in PROC MIXED).

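### The per-visit PRO ANCOVA and the random coefficient models omit both randomization stratification factors; if those factors predict PRO scores, between-arm standard errors are modestly conservative

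*SAP*

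**What the plan says.** SAP 3.4.2 states: "Randomization is stratified by the following, as recorded in the Interactive Response Technology (IRT) system". It lists two binary factors. One is best response to first-line chemotherapy (complete or partial response against stable disease). The other is "Metastatic disease site (visceral vs. non-visceral) at the time of initiating first-line chemotherapy".

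Two model families are planned for the FBISI-18 total, its four subscales, EQ-5D-5L and EQ-VAS:

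- **Per-visit ANCOVA (SAP 6.2.7.4, Descriptive Summary).** "The adjusted means (ie LS-MEANS) will be obtained from ANCOVA model that included baseline score and treatment as independent variables". Output is by arm: "For each per-visit analysis, the n, LS-mean, standard error, and 95% CI will be reported".
- **Random coefficient models (SAP 6.2.7.6).** Here "the predictors are the corresponding baseline PRO score, treatment, time (treated as a continuous variable), and treatment-by-time interaction". On the random side, "Intercept and time are considered as random effects particular to each patient".

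Neither list contains a stratification factor. For the DRS-P subscale of the same instrument, SAP 6.2.7.5 says "TTD will be analyzed by a log-rank test stratified by randomization stratification factors". OS (SAP 6.1.1.1) and PFS (SAP 6.2.2.1) have stratified log-rank tests and stratified Cox models, and objective response (SAP 6.2.2.3) has a Cochran-Mantel-Haenszel test across the strata. SAP 3.4.2 limits the use of other baseline characteristics as covariates. That sentence concerns variables other than these two, so it does not explain the omission.

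**The concern.** Stratified randomization makes the arms nearly equal in stratum mix, so stratum differences contribute little to the real sampling variation of a treatment difference. A model without the strata still counts those differences as residual noise. Its standard error for the difference is then larger than the true one, to the extent that the strata predict the score after baseline is accounted for.

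There is a second, separate reason to adjust. Balance is arranged at randomization, in all patients. PD-L1 status is determined retrospectively and is not a stratification factor, and the set of patients completing questionnaires shrinks over time. In the PD-L1-positive population and at later visits, some imbalance on the strata can therefore arise, and these models would not remove it.

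PRO evaluation is a secondary objective in both co-primary populations, and Protocol 9.3.2 plans between-group comparisons of symptom improvement.

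**Working it through.** **The plan's own figures.** The documents give no standard deviation, power or sample size for any PRO model. Their only sizing figures are for OS. They reproduce with power = Φ(√d/2 × |ln HR| − z):

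- All patients: √425/2 × 0.3567 − 2.170 = 1.506, so 93.4% (stated 93%).
- PD-L1-positive: √219/2 × 0.4308 − 2.326 = 0.861, so 80.5% (stated 80%).

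The present point does not touch either figure.

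**ANCOVA, between-arm difference.** Let R² be the share of variance remaining after baseline score that the strata explain. With balanced strata, SE(omitted)/SE(included) = 1/√(1 − R²). R² is not in the documents, so a range is assumed.

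| R² | SE ratio |
|---|---|
| 0 | 1.000 |
| 0.01 | 1.005 |
| 0.05 | 1.026 |
| 0.10 | 1.054 |
| 0.20 | 1.118 |

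A simulation checked this. It assumed stratified permuted blocks of four, stratum prevalences of 30% and 50%, and a baseline coefficient of 0.6. At n = 668, model SE divided by empirical SE with strata omitted was 1.02, 1.05 and 1.11 at R² = 0.05, 0.10 and 0.20. With strata included it was 1.00 each time. Two-sided error at nominal 5% was 4.0% omitted against 5.35% included at R² = 0.10, and 3.2% against 4.9% at R² = 0.20. At R² = 0 both models gave about 4.3%, which shows the size of the simulation noise.

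**Random coefficient model.** The formula above does not carry over, because the strata act on only one of several variance components. Assume six monthly visits (mean time 3.5, sum of squares about the mean 17.5), intercept variance 0.5, slope variance 0.01, no covariance between them, and residual variance 0.4. With complete data:

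- The per-patient variance for the average effect is 0.5 + 0.01 × 3.5² + 0.4/6 = 0.6892.
- If the strata explain 10% of intercept variance, this becomes 0.45 + 0.1225 + 0.0667 = 0.6392. The SE ratio is √(0.6892/0.6392) = 1.038.
- At 1% the ratio is √(0.6892/0.6842) = 1.004. At 5% it is √(0.6892/0.6642) = 1.019.
- The per-patient variance for the slope is 0.01 + 0.4/17.5 = 0.0329. Intercept variance does not enter, so the ratio for treatment-by-time is 1.000 throughout.

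**Arm-level adjusted means.** These are what SAP 6.2.7.4 actually reports. In the simulation at n = 668, over R² from 0 to 0.20, model SE divided by empirical SE with strata omitted was 1.01 to 1.04 when baseline was unrelated to outcome. It was 0.91 to 0.97 with a baseline coefficient of 0.6. The direction is not fixed. With strata included and a coefficient of 0.6, the ratio was 0.86 to 0.93, so adding strata does not calibrate these standard errors.

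**The case against.** A reader might infer that every PRO standard error in these sections is too large. The documents do not support that, for three reasons.

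- The inflation needs the strata to be prognostic beyond the baseline score, which both models already contain. The documents give no evidence on this, and with no such association there is no inflation.
- SAP 6.2.7.4 is a descriptive section that reports arm means and names no between-arm difference or test. Those arm-level standard errors can be too small as well as too large.
- The treatment-by-time term in SAP 6.2.7.6 is essentially unaffected.

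All three stand and limit the point to between-arm comparisons.

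It can also be said that the comparison with OS, PFS and response is not like for like. Their stratified analyses are between-arm, while their arm-level summaries (Kaplan-Meier estimates, exact response intervals) are unstratified. That is fair for the arm means. It does not cover the treatment effect in SAP 6.2.7.6, or a difference taken from the ANCOVA.

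The two reasons for adjusting also pull in different directions: conservatism depends on balance, whereas removing imbalance matters once balance is lost. Both favour including the strata, but they should not be added together as one harm.

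Finally, no alpha is allocated to PROs, Protocol 9.3.2 lists repeated-measures modelling among optional exploratory analyses, and the error in a balanced comparison is conservative. This keeps the point minor.

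**Conclusion.** The omission is real, unexplained, and inconsistent with the stratified between-arm analyses elsewhere in the SAP, including the one on the DRS-P subscale. The consequence is conditional and small. For a between-arm difference from the ANCOVA, the standard error is overstated by 0% to 5.4% over R² from 0 to 0.10. For the average treatment effect in the random coefficient model the overstatement is about 0.4% to 4% when the strata explain 1% to 10% of intercept variance. The R² values, variance components, visit pattern, stratum prevalences and block size are assumptions, not figures from the documents. The finding does not extend to the treatment-by-time slope or to arm-level adjusted means. It affects no decision on the primary endpoint and is best treated as an inexpensive improvement.

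**What to change.** Add best response to first-line chemotherapy and metastatic site, as recorded in the IRT system, as fixed effects to the ANCOVA in SAP 6.2.7.4 and to the random coefficient models in SAP 6.2.7.6.

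State in the SAP that adjusted means use observed margins. With class factors in the model, the default weights factor levels equally, which would move the arm means away from the trial's actual stratum mix. In a main-effects model this choice does not alter the between-arm difference.

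The cost is two terms, hence two degrees of freedom, in each model. That is negligible against about 668 randomized patients (at least 334 estimated PD-L1-positive). It is slightly more noticeable at late visits with few completers, because the ANCOVA is fitted separately at each visit. If the sponsor prefers to leave the factors out, the SAP should say why.
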